Title: Immune-Related Trafficking and Signaling in Human Skin Associated with Low-Power, Infrared Laser Treatment

ClinicalTrials.gov: NCT02453113

ID: NIH/LAMMP-2015-1840

PROTOCOL NARRATIVE FOR EXPEDITED OR FULL COMMITTEE RESEARCH

University of California, Irvine Institutional Review Board

Version: April 2013

HS#: 2015-1840 For IRB Office Use Only

Lead Researcher Name: [name].

Study Title: Immune-Related Trafficking and Signaling in Human Skin Associated with Low-Power,

Infrared Laser Treatment

NON-TECHNICAL SUMMARY

Provide a non-technical summary of the proposed research project that can be understood by IRB members with varied research backgrounds, including non-scientists and community members. The summary should include a brief statement of the **purpose of the research** and **related theory/data supporting** the intent of the study as well as a brief description of the **procedure(s) involving human subjects**. *This summary should not exceed* ½ **page.**

Recently, a group of scientists have reported that shining a specific kind of laser on the skin may improve the immune response to a vaccine. This study aims to further investigate the body's response to shining a certain type of light on the skin. It is hoped that the results of this study could then be used to determine if a laser may improve the response to a vaccine.

For these studies, we will recruit 10 healthy adults ages 18-50 from the patient population at the Beckman Laser Institute in Irvine, CA. We will treat the skin of the lower back with a predetermined tolerable laser setting. Once this is done, small tissue samples will be analyzed to further understand the body's response to the laser in hopes that this response may help improve the body's response to vaccines.

SECTION 1: PURPOSE AND BACKGROUND OF THE RESEARCH

- 1. Describe **the purpose of the research** project and state the overall objectives, specific aims, hypotheses (or research question) and scientific or scholarly rationale for performing the study.
- 2. Provide the **relevant background information** on the aims/hypotheses (or research question) to be tested and the procedures/products/techniques under investigation.
- 3. Include a description of the **primary outcome variable(s)**, **secondary outcome variables**, **and predictors** and/or comparison groups as appropriate for the stated study objectives.
- 4. Include a critical evaluation of **existing knowledge**, and specifically identify the information gaps that the project intends to address.
- Describe previous research with animals and/or humans that provides a basis for the proposed research. Include references/citations, as applicable. This section should not exceed 4 pages.

The purpose of this proposal is to demonstrate that CW NIR laser treatment of human skin induces changes in cytokine and chemokine signaling in the skin and results in a statistically

significant increase in the number of dendritic cells in the skin tissue at the site of laser treatment. The hypothesis behind this result is that the human skin immune system will respond to low level 1064 nm light in a similar manner to mice.

Specific Aim: Demonstrate that a non-painful and non-damaging dose of CW NIR laser results in alteration of cyotkine and chemokine signaling and a significant increase in the number of dendritic cells in skin tissue exposed to the laser.

A published study showed that one-minute exposures of mouse skin to a 1064 nm laser light delivered at non-painful and non-damaging parameters resulted in significant immunologic changes in the skin that included up-regulation of specific cytokine and chemokine genes and the activation and mobilization of specific dendritic cells (Kashiwagi *et al.* 2013). We will assess whether 1064 nm laser treatment of human skin at roughly equivalent parameters evokes similar patterns of cytokine/chemokine signaling and immune cell activity.

It has been demonstrated in a published study that 1064 nm laser light delivered at a power, irradiance, duration and dose roughly equivalent to that used in mouse vaccine studies was tolerated and non-damaging to humans (Kashiwagi et al. 2013).

We will enroll 10 volunteers with skin phototypes I/II. Skin phototypes will be determined by [name] (board certified dermatologist). It has been shown that lighter and darker skin types respond differently to 1064 nm wavelength light (Leclere et al. 2012) and choosing either lighter or darker skin types to study initially will reduce variability and will help eliminate confounding variables. Thus, skin phototypes I/II will be studied for our pilot human study.

In the first part of the study, we will make a determination of the laser irradiance that will be tolerated by all study subjects (as measured by lack of discomfort over the whole 1 minute exposure). Each subject will receive up to five initial one-minute treatments at 1, 2, 3, 4, and 5 W/cm² (0.2, 0.4, 0.6, 0.8 and 1 Watt). If a subject experiences discomfort at any of these irradiances, a second set of exposures will be made between the highest tolerable irradiance and the one that was not tolerable. These will be done at 0.2 W/cm² increments (e.g., 3.2, 3.4, 3.6, and 3.8 W/cm²). The highest irradiance the subject tolerates for 1 minute will be identified as that subject's maximum tolerable irradiance. After all subjects are tested, we will select the highest irradiance that was tolerated by all ten subjects and use this in the second phase of the study. The determination of the maximum tolerable irradiance of all 10 subjects will be determined before starting the second phase of the study below.

Within 6 months after the first test exposures and determination of the universal maximum tolerable irradiance, each subject will receive a one minute laser treatment at the maximum tolerable irradiance. Four hours later, we will take two 4 mm punch biopsies from bilateral areas of the lower back. One biopsy will be taken from the skin area treated by the laser, and one from an untreated area on the other side of the back as a control. Each biopsy sample will be divided into two using a sterile scalpel. One half of each sample will be immersed in formalin and shipped to the Massachusetts General Hospital Dept. of Dermatopathology for processing, fixing, and embedding in paraffin for determination of specific immune cell populations using specific immunohistochemical staining. The samples will also be stained with Hematoxylin and Eosin for histology at Massachusetts General Hospital Dept. of Dermatopathology. The other half of each sample will be flash frozen at -80° C for subsequent qPCR to identify upregulation of specific cytokines and chemokines such as IL-1a, IL-1b, TNFa, CCL2, CCL6, CCL11, CCL17, CCL19, CCL20, and CCR7. After flash freezing, this tissue will be sent to the Massachusetts General Hospital Vaccine and Immunotherapy Center for processing.

There will be a total of 5 visits, about 10-11 hours over a maximum period of 18-19 weeks in length of the study. Those visits include a screening visit, a visit assessing laser tolerance, a follow-up visit within 20-48 hours of tolerability testing to ensure patient safety, a treatment visit

with resultant biopsy, and a follow-up visit after biopsy to ensure patient safety.

References:

Expected Results and Data Analysis:

We expect to demonstrate that this NIR laser dose elicits statistically significant dendritic cell trafficking to the human skin and induces cytokine/chemokine release and expression changes similar to that previously seen in mice.

The statistical end point of the study will be the changes in density of CD11c+ dermal dendritic cells between two biopsies from a study subject where one sample is subjected to laser irradiation and the other is the control. For assessment of statistical significance, we will apply a paired sample t-test.

SECTION 2: ROLES AND EXPERTISE OF THE STUDY TEAM

List all study team members below.

- 1. Identify each **member's position** (e.g., Associate Professor, graduate or undergraduate student) and **department**, and describe his or her **qualifications**, **level of training and expertise**. Include information about relevant licenses/medical privileges, as applicable.
- 2. Describe each team member's **specific role and responsibility** on the study.
- 3. **Faculty Sponsors** list as Co-Researchers and describe their role on the project; include oversight responsibilities for the research study.
- 4. Explain who will have access to subject identifiable data.
- 5. Indicate who will be involved in recruitment, informed consent process, research procedures/interventions, and analysis of data.

Lead Researcher:

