 - a. Include an explanation of the study design (e.g., randomized placebo-controlled, cross-over, cross-sectional, longitudinal, etc.) and, if appropriate, describe stratification, randomization, and blinding scheme.
 - b. Provide precise definitions of the study endpoints and criteria for evaluation; if the primary outcomes are derived from several measurements (i.e., composite variables) or if endpoints are based on composite variables, describe precisely how the composite variables are derived.
 - c. Indicate how much time will be required of the subjects, per visit and in total for the study.
 - d. Indicate the **setting where each procedure will take place**/be administered (e.g. via telephone, clinic setting, classroom, via email). **Note:** If any of the procedures will take place at off-campus locations (e.g., educational institutions, businesses, organizations, etc.) **Letters of Permission** are required.
 - e. If a procedure will be completed more than once (e.g., multiple visits, pre and post survey), indicate **how many times** and the **time span** between administrations.
- 2. For studies that involve routine (standard of care) medical procedures:
 - Make clear whether procedures are being done for clinical reasons or for study purposes, including whether the procedures are being done more often because of the study. Use the following guidelines to determine the extent to which standard procedures and their associated risks need to be described in protocol:
 - a. If the standard procedure is not explicitly required by the study protocol, the protocol need not describe that procedure or its risks.
 - b. If the standard procedure is a main focus of the study (e.g., one or more arms of a randomized study is standard) or is explicitly required by the study protocol, the protocol must include a full description of the procedure and its risks.]
- 3. It is **strongly recommended** that you include a table of visits, tests and procedures. Tables are easier to understand and may help to shorten long repeated paragraphs throughout the narrative.
- 4. If study procedures include collecting photographs, or audio/video recording, specify whether any

- subject identifiable information will be collected and describe which identifiers will be collected, if any.

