Prior to all laser treatments, female patients of childbearing age will be administered a urine Beta hCG urine test. A positive result will disqualify the patient from the study. These results will be intended for research purposes only and will not be included in the patients' medical record.

A 95% water polymer gel will be applied prior to all laser treatments to all laser-exposed skin in order to limit excessive heat buildup within the skin. The gel will also be applied to the control site non-treated skin that will be biopsied. Subjects and research personnel will wear protective goggles appropriate to the safety rating of the laser.

In order to determine the maximum tolerable laser irradiance to be used in the biopsy phase of the study, each subject will receive a series of 1 minute exposures on 5 mm² areas of the skin of the lower back from continuous wave 1064 nm laser light emitted by a modified handheld diode laser device (IPG Photonics). Prior to these treatments, subjects will be informed about the kind of skin sensations the laser may cause and will always be asked to indicate to the study doctor when the exposure becomes uncomfortable. In the case that an exposure produces discomfort in the subject (a tingling or pinprick sensation or uncomfortable feeling of hotness), the exposure will be terminated. After the completion of each test site, the study personnel will examine the skin surface for signs of damage or alteration. Digital photographs will be taken of all sites before and after laser treatment.

Up to five initial one-minute treatments will be given to each subject starting at 1 W/cm² and increasing at 1 W/cm² increments up to a maximum of 5 W/cm² (0.2, 0.4, 0.6, 0.8 and 1 Watt). If a subject experiences discomfort during any of these treatments, a second set of treatments will be made between the highest tolerable irradiance and the one that was not tolerable. These will be done at 0.2 W/cm² increments (e.g., 3.2, 3.4, 3.6, and 3.8 W/cm²). The highest irradiance the subject tolerates for 1 minute will be identified as that subject's maximum tolerable irradiance. After all subjects are tested, we will select the highest irradiance that is tolerated by all ten subjects and use this in the second phase of the study.

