The determination of maximum tolerable irradiance will be conducted within 6 months of the second phase of the study. At that time, all subjects will receive a single treatment to a 5 mm spot on the lower back with the CW NIR laser for one minute at the maximum tolerable irradiance. The determination of the maximum tolerable irradiance of all 10 subjects will be determined before starting the second phase of the study.

Within 20-48 hours, patients will return to clinic for a follow-up visit where the treated site will be checked to ensure no unusual reactions from the treatment have occurred.

2. Punch Biopsy

Four hours later, two 4 mm punch biopsies will be performed on the skin of the lower back: one at the location of the laser exposure (experimental) and a second one at a bilateral non-exposed skin site on the lower back (control). Biopsies will be taken using standard biopsy protocol. The skin will be cleaned and patient will receive local anesthesia for this procedure. Following completion of the biopsies, a bandage will be placed on each biopsy site. The clinical research personnel will provide the subject instructions in oral and written form on the care of the biopsy site. The subject will be seen 10-14 days after to assess the status of the biopsy site for proper healing.

In summary, there will be a total of 5 visits, about 10-11 hours total, spanning over a maximum of 18-19 weeks in length of the study. Those visits include a screening visit, a visit assessing laser tolerance, a follow-up visit within 20-48 hours of tolerability testing to ensure patient safety, a treatment visit with resultant biopsy, and a follow-up visit or phone call including photos of biopsy sites after biopsy to ensure patient safety.

3. Tissue Analysis

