Half of each biopsy sample will be fixed, paraffin embedded and prepared as thin section slides. One set of these slides will receive Hematoxylin and Eosin staining to evaluate microscopic skin changes. This analysis will be conducted by faculty affiliated with the Massachusetts General Hospital Dept. of Dermatopathology after receiving the biopsy samples immersed in formalin from UC Irvine. A second set of specimen slides, identified only by subject number, will also be sent to collaborators at the Massachusetts General Hospital Dept. of Dermatopathology for further immunohistochemical staining and analysis. The second half of each biopsy specimen will be flash frozen at -80 C. These samples will be identified only by subject number and sent to collaborators at the Massachusetts General Hospital Vaccine and Immunotherapy Center for assessment of RNA and protein expression by qPCR, which will be used to identify up-regulation of specific cytokines and chemokines such as IL-1a, IL-1b, TNFa, CCL2, CCL6, CCL11, CCL17, CCL19, CCL20, and CCR7.

B. Statistical Considerations

- 1. **Statistical Analysis Plan:** Describe the statistical method(s) for the stated specific aims and hypotheses **described in Section 1**. *Note:* Required for scientific review.
- 2. **Explain how the overall target sample size was determined** (Provide power / sample size justification for the study).

If a statistical analysis plan is not appropriate for your study design, please describe a plan for assessing your study results.

Statistical Plan and Data Analysis:

Ten subjects will be recruited for the study on skin immune response to laser treatment. This is a single-site pilot study and all subjects will be recruited through their affiliation with the researchers. Analysis of histology samples of the skin will be for exclusion of indications of skin damage and will not be used in statistical analyses. Analysis of RNA and protein expression by qPCR will be descriptive and not used in statistical analyses.

Quantitative analysis will pertain to changes in the density of CD11c+ dermal dendritic cells in the laser-treated skin as compared with non-laser treated control skin. For assessment of statistical significance, we will apply a paired sample t-test.

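### No random allocation of the lasered side is described, so a consistent left-right or site-choice difference would be confounded with the laser effect

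*Combined protocol and SAP*

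**What the plan says.** Section 1 describes the biopsy phase thus: "One biopsy will be taken from the skin area treated by the laser, and one from an untreated area on the other side of the" (lower back). Under Punch Biopsy in the methods, the control biopsy is "a second one at a bilateral non-exposed skin site on the lower back (control"). Under Laser Treatment, "all subjects will receive a single treatment to a 5 mm spot on the lower back", with no side and no rule for choosing the spot. The same heading equalises one factor: "The gel will also be applied to the control site non-treated skin that will be biopsied".

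The instructions on the form for Section 3 ask the author, if appropriate, to "describe stratification, randomization, and blinding scheme". The Study Design text that answers them, and the statistical plan in Section 3B, give no scheme for the side.

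The endpoint is "changes in density of CD11c+ dermal dendritic cells between two biopsies from a study subject", and "For assessment of statistical significance, we will apply a paired sample t-test". Each side is biopsied once, four hours after exposure. No pre-exposure biopsy is planned.

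In the earlier tolerance phase, "each subject will receive a series of 1 minute exposures on 5 mm² areas of the skin of the lower back". Again no side is stated.

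**The concern.** Pairing removes differences between subjects. It does not remove a difference between the two sites of one subject that lines up with treatment. The paired t-test credits the whole mean difference to light, and this is justified only if, before exposure, the skin to be lasered was as likely to have the higher cell density as the control skin. A baseline biopsy could test that, and random allocation of the side would secure it. The plan has neither.

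Two kinds of difference could run consistently with treatment. One is a left-right difference, if the same side is lasered in most or all subjects. The other is a site-choice difference, if one kind of skin patch tends to be taken for treatment and another for control. The tolerance phase adds a possible source. Several test exposures are made in the same body region up to six months earlier, and nothing says how those spots lie relative to the later treated and control sites.

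The stated aim is to demonstrate a statistically significant increase in dendritic cells. The p-value therefore carries the main conclusion, although the study is called a pilot.

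**Working it through.** **Inputs from the documents.** Ten subjects; p value 0.05; power at least 80%; SD of differences 1.0; expected change about 108% (Sections 3B and 4A). The paired t-test is not stated to be one- or two-sided; two-sided is assumed. The SD has no stated unit; it is read on the same scale as the effect, so that 1.0 is 100% of control density.

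**The plan's own figure.** The standardised effect is d = 1.08 / 1.0 = 1.08. Power is P(|T| > t(0.975, n−1)), where T is noncentral t with n−1 degrees of freedom and noncentrality d√n.

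- n = 8: 74.6%
- n = 9: 80.9%
- n = 10: 85.9%

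The plan's nine subjects are reproduced. The sample size is not the problem here.

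**Effect of a consistent offset.** Assume no laser effect and a constant lasered-minus-control offset of b SD of the differences. The same formula applies with noncentrality b√10, 9 degrees of freedom and critical value 2.262. For comparison, the side was randomised in simulation, independently per subject or by a list of 5 left and 5 right, with a left-right difference of the same size b.

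| Assumed b | b√10 | False positives, consistent offset | Side randomised per subject | 5/5 list |
|---|---|---|---|---|
| 0.1 | 0.316 | 5.9% | about 5% | 4.9% |
| 0.2 | 0.632 | 8.8% | about 5% | 4.6% |
| 0.3 | 0.949 | 13.6% | about 5% | about 4% |
| 0.5 | 1.581 | 29.3% | about 5% | 3.0% |

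The 5/5 list falls below 5% because the side difference cancels in the mean but still widens the estimated SD.

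**If the offset runs against the laser.** With a true effect of 1.08 and a consistent offset of −b, d becomes 1.08 − b. Power at n = 10 falls from 85.9% to 78.7%, 69.8%, 59.5% and 37.4% for b = 0.1, 0.2, 0.3 and 0.5.

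**Power cost of randomising, if a side difference exists.** With the side randomised per subject, simulated power for the 1.08 effect is about 85.5%, 84.7%, 82.9% and 77.6% for the same b values, against 85.9% when there is no side difference.

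**Scale in cells.** The plan cites a control density of 73 cells per mm. If the SD of differences is 100% of that, b = 0.1, 0.2, 0.3 and 0.5 are 0.1 × 73 = 7.3, then 14.6, 21.9 and 36.5 cells per mm. The plan also cites a standard error of about 10 cells in 15 volunteers, which implies a between-person SD of 10 × √15 = 38.7 cells. If the SD of differences were nearer that value, which is also an assumption, the same b values would be about 3.9, 7.7, 11.6 and 19.4 cells per mm.

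**The case against.** The documents are silent; they do not describe a biased procedure. A reader might infer that the operator picks the side at the visit after looking at the skin. Nothing in the text says who chooses, when, or by what rule, and a fixed-side convention fits equally well. A reader might also infer that holding the device on one site only is a further difference. The text calls the device handheld but does not say that it touches the skin, nor what is done at the control site beyond applying gel. It likewise does not show the order of the two biopsies to be a problem. These stronger readings are not supported.

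The design already controls a good deal. Both sites are in the same person and the same region, they are biopsied at the same visit, and gel goes on both. The form asks for randomisation only where appropriate, and this is a ten-subject pilot. On the 100%-of-control scale, an offset of 0.5 SD means that one side of healthy lower-back skin carries on average half the baseline density more than the other, and nothing in the documents points to that. At 0.1 SD the error rate barely moves. Part of the document, just before the form instructions for Section 3, is absent from the public text. It probably lists study staff, but that cannot be checked.

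All of this limits the likely size and the mechanism. It does not supply an allocation rule, and the confounding remains whether the operator chooses or a fixed side is used.

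**Conclusion.** The point holds as a gap in the design: no random allocation of the lasered side is described, and there is no baseline biopsy to show that the sites started equal. Any side or site-choice difference that consistently favours one direction would be inseparable from the laser effect. Choices that vary haphazardly between subjects would add variance and cost power, but would not bias the mean.

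The false-positive rates of 5.9% to 29.3% illustrate assumed offsets of 0.1 to 0.5 SD. They rest on a two-sided test, normally distributed differences and a constant offset, and they do not estimate bias in this trial. It would go too far to conclude that the result will be biased, or biased by a particular amount. What can be said is that the plan leaves open a source of error that it could close at almost no cost, and that cannot be closed once the biopsies have been taken.

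**What to change.** In Section 3A, state three things:

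1. Mirror-image left and right lower-back sites, both clear of the phase 1 test spots, are marked first.
2. The side to be lasered is then revealed from a list generated in advance, for example 5 left and 5 right.
3. The lasered side is recorded for each subject.

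Marking both sites before the side is revealed deals with site choice; the list deals with left-right differences. Keeping clear of the test spots also means that the control skin was not itself exposed in phase 1.

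The cost is a one-page list. It needs no added subjects, biopsies or laser exposures. If a real side difference exists, some power is lost under per-subject randomisation: about 3 percentage points at 0.3 SD (85.9% to 82.9%) and about 8 at 0.5 SD (85.9% to 77.6%). The loss with a 5/5 list is slightly smaller. If there is no side difference, nothing is lost.
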